All participants must have routine imaging performed to verify treatment set up. The minimum imaging requirement is once weekly orthogonal KV images commencing on the first day of treatment and reviewed by the managing radiation oncologist. Centers are strongly encouraged to employ daily volumetric image guidance with either accelerator mounted KV or MV cone beam CT or tomotherapy CT images utilizing matching of bony anatomy. The margin for PTV can be reduced to 3 mm if daily IGRT is performed.

Table 11 details radiotherapy compliance criteria.

Table 11 Radiotherapy Compliance Criteria

	Per Protocol	Variation Acceptable	Deviation Unacceptable
Prescription Dose	Delivered daily or total dose to any PTV is within 5% of the protocol dose.	Delivered daily or total dose to any PTV differs from the protocol specified dose by 6-10%	Delivered daily or total dose to any PTV differs from the protocol specified dose by >10%
Dose Uniformity	Dose to 95% of any PTV is > 95% of prescribed dose.	Dose to 95% of any PTV <95% of the prescribed dose; >10% of the highest dose PTV >110% of prescribed dose	Dose to 95% of any PTV <90% of the prescribed dose; >10% of the highest dose PTV >120% of prescribed dose
Volume	Volumes follow protocol guidelines	PTV margins are less than the protocol specified margins or excessively large	CTV does not encompass areas at risk.
Organs at Risk			Dose to 2% of PRV spinal cord >50 Gy Dose to 2% of PRV brainstem >54 Gy
Interruptions		Uncompensated Interruptions more than 2 days for reasons other than toxicity	Uncompensated Interruptions more than 10 days for reasons other than toxicity
Abbreviations: CTV = clinical target volume; PRV = Planning Organ at Risk Volume; PTV = planning target volume.			

9.1.10.1.2.3 Supportive Care for Head and Neck Radiotherapy

Radiation-induced head and neck toxicity is well known and has been well described. It is expected to vary according to the total dose and the concomitant use of chemotherapy. Locoregional toxicity will be monitored during treatment using CTCAE v. 4.0 and will be reported in the database. Supportive care will be provided according to local SoC.

Reversible mucositis and pharyngitis is expected, and supportive care will be initiated (eg, pain medication, mouth wash, adaptation of the diet, use of a nasogastric or percutaneous endoscopic gastrostomy feeding tube). In very rare cases of severe Grade 4 mucositis (eg, bleeding); it may be necessary to interrupt RT for a few days. However, it is mandatory to limit the break to a strict minimum.

Various degrees of skin reaction (typically Grade 2, less frequently Grade 3) are expected in the treated area. Other expected acute reactions include fatigue, xerostomia, dysgeusia, ageusia and dysphagia.

Central nervous system events in terms of nausea and vomiting are expected. Late effects include some degree of xerostomia and occasionally persistent dysphagia.

Mandibular osteoradionecrosis may occur in less than 5% of the participants. Thorough dental evaluation and, if necessary, adequate care performed before the start of RT, will substantially decrease this risk.

9.1.10.1.2.4 Treatment Interruptions / Modifications

Treatment interruptions are to be avoided unless medically necessary. Any breaks in RT should be minimized. See Section 7.2.2 – Dose Modification for Radiotherapy.

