7.1 Treatments Administered

The study treatment(s) to be used in this trial are outlined below in [Table 2](#).

Refer to Appendix 8 for country-specific requirements.

Table 2 Study Treatment(s)

Arm Name	Arm Type	Intervention Name	Intervention Type	Dose Formulation	Unit Dose Strength(s)	Dosage Level(s)	Route of Administration	Regimen/ Treatment Period	Use	IMP/ NIMP/ AxMP	Sourcing
Arm A	Experimental	Pembrolizumab	Drug	Solution for infusion	100 mg/vial	200 mg	IV infusion	Q3W for up to 17 cycles	Test Product	IMP	Central
Arm A	Experimental	Radiotherapy	Radiation	NA (Radiation)	2 Gy/fraction	2 Gy/day	Internal radiation - systemic	Low-risk participants: 2 Gy/day in 30 fractions for a total of 60 Gy High-risk participants: 2 Gy/day in 33 fractions for a total of 66 Gy Participants with gross residual disease: 2 Gy/day in 35 fractions for a total of 70 Gy	Background treatment	NIMP/ AxMP	Local
Arm A	Experimental	Cisplatin	Drug	Solution for infusion	1 mg/mL	100 mg/m ²	IV infusion	Q3W for 3 cycles	Test Product	IMP	Local or central
Arm B	Active comparator	Radiotherapy	Radiation	NA (Radiation)	2 Gy/fraction	2 Gy/day	Internal radiation - systemic	Low-risk participants: 2 Gy/day in 30 fractions for a total of 60 Gy High-risk participants: 2 Gy/day in 33 fractions for a total of 66 Gy Participants with gross residual disease: 2 Gy/day in 35 fractions for a total of 70 Gy	Background treatment	NIMP/ AxMP	Local

Arm Name	Arm Type	Intervention Name	Intervention Type	Dose Formulation	Unit Dose Strength(s)	Dosage Level(s)	Route of Administration	Regimen/ Treatment Period	Use	IMP/ NIMP/ AxMP	Sourcing
Arm B	Active comparator	Cisplatin	Drug	Solution for infusion	1 mg/mL	100 mg/m ²	IV infusion	Q3W for 3 cycles	Test Product	IMP	Local or central

Abbreviations: AxMP=auxiliary medicinal product; EEA =European Economic Area; IMP=investigational medicinal product; IV=intravenous; NA=not applicable; NIMP=noninvestigational medicinal product; Q3W=every 3 weeks.

The classification of IMP and NIMP/AxMP in this table is based on guidance issued by the European Commission and applies to countries in the EEA. Country differences with respect to the definition/classification of IMP/NIMP/AxMP may exist. In these circumstances, local legislation is followed.

Pembrolizumab and cisplatin are allowed to be given on the same day.

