9.1.10.1.2 Radiotherapy

It is recommended that RT is started within 6 weeks after surgery. All participants in the study will be treated with 6 to 10 MV photons. The administration of standard fractionated RT regimen should follow the dose parameters in [Table 8](#). Linear accelerator or Tomotherapy based equipment is allowed. Use of intensity modulated radiation therapy (IMRT) is required, with either a sequential boost technique or Simultaneous Integrated Boost (SIB-IMRT).

Center credentialing will be performed according to criteria defined in the RT QA Manual. Participating institutions must comply with the RT QA requirements and procedures described in the RT QA manual. Sites that do not conform to the requirements of the credentialing will not be allowed to participate.

Both static and dynamic techniques IMRT techniques (including VMAT) are allowed. Dose planning, prescription, specification and reporting will be done according to International Commission on Radiation Units (ICRU) report 83 recommendations. Dose-volume constraints will be used for both dose specification and dose reporting in planning target volume (PTV) and planning organs at risk volumes (PRV)/organs at risk (OAR) (see Section 9.1.10.1.2.1). The dose-volume objectives that will be used for planning, dose specification and dose reporting in PTV, PRV and OAR are described in Section 9.1.10.1.2.1.

Table 8 Radiotherapy Dose Parameters

	Sequential Boost Plan	Simultaneous Integrated Boost (followed by additional boost if needed)
Low Risk for Microscopic Disease ^a	50 - 54 Gy in 25 - 27 fractions	54 Gy in 30 fractions
Intermediate Risk for Microscopic Disease ^b	60 Gy in 30 fractions	60 Gy in 30 fractions
Regions at High Risk ^c	66 Gy in 33 fractions	66 Gy in 33 fractions
Gross Residual Tumor ^d	70 Gy in 35 fractions	70 Gy in 35 fractions

CTV=clinical target volume; GTV=gross tumor volume; IGRT=image guided radiation therapy; PTV=planning target volume; RT=radiotherapy.

a. CTV_5000 or CTV_5400 defined as the area that is low risk for microscopic disease. This is the non-dissected neck. This RT dose is applicable for participants in the low-risk and high-risk groups.

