b. CTV_6000 defined to include the post-operative tumor bed and nodal regions at risk of microscopic spread that have not been operated on according to standard anatomic guidelines relative to location and extent of gross disease. Please note all operated sites should receive 60 Gy. This RT dose is applicable for participants in the low-risk and high-risk groups.

c. CTV_6600 defined to include 0.5 cm expansion on regions thought to be at high risk of recurrence (eg, areas of extranodal extension or positive margins of resection). This RT dose is applicable for participants in the high-risk group.

d. For participants who do not undergo planned curative surgery or for incomplete resection with gross residual tumor: primary surgical tumor bed encompassing preoperative GTVs plus up to 0.5 cm to define CTV_7000.

All PTVs defined as 0.3 to 0.5 cm expansions on CTVs based on method and frequency of IGRT.

Radiotherapy treatment for participants that undergo surgery will be delivered over 6 to 6.5 weeks, depending on risk of recurrence, by incorporating 5 fractions per week (example: 5 fractions over 5 days (1 fraction per day), 2 days off).

Participants that do not undergo surgery as planned, for whatever reason, and proceed directly to salvage CRT may receive a RT dose of 70 Gy (total of 35 fractions) over 6.5 to 7 weeks.

When Sequential Boost IMRT is used, planning and delivery should be as follows: 50 Gy in 25 fractions or 54 Gy delivered in 27 fractions of 2 Gy/fraction, followed by a boost of 6 Gy in 3 additional fractions of 2 Gy/fraction. If an additional boost is required for high risk area such as areas of extranodal extension and/or positive margins, an additional 6 Gy can be delivered in 2 Gy/fraction in 3 fractions.

If SIB-IMRT is used, potential planning and delivery can be as follows: 60 Gy delivered in 30 fractions of 2 Gy/fraction given simultaneously with 54 Gy in 1.8 Gy/fraction. If an additional boost is required for high risk area such as areas of extranodal extension and/or positive margins, an additional 6 Gy can be delivered in 2 Gy/fraction for 3 fractions.

If all of the surgical area is considered at high risk for disease recurrence, another potential prescription option can be 66 Gy fractions given in 33 fractions at 2 Gy/fraction.

If gross disease is identified, in the case of a participant with incomplete resection, an additional boost up to 70 Gy may be delivered to the gross disease area.

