10.12 Extent of Exposure

Extent of exposure for a participant is defined as number of cycles in which the participant receives the study treatment infusion. Summary statistics will be provided on Extent of Exposure for the APaT population.

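### The sequential-boost radiotherapy instruction gives 56 Gy and 62 Gy from its 50 Gy start, 4 Gy below the 60 Gy and 66 Gy required elsewhere in the protocol

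*Combined protocol and SAP*

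**What the plan says.** For sequential-boost IMRT, Section 9.1.10.1.2 sets out how planning and delivery should proceed: "50 Gy in 25 fractions or 54 Gy delivered in 27 fractions of 2 Gy/fraction, followed by a boost of 6 Gy" in 3 fractions of 2 Gy. For high-risk areas, such as extranodal extension or positive margins, "an additional 6 Gy can be delivered in 2 Gy/fraction in 3 fractions". One boost is thus given for two different starting doses.

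The required totals appear in several other places:

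- Table 8 (same section), sequential column: "50 - 54 Gy in 25 - 27 fractions" for the low-risk, non-dissected neck; 60 Gy in 30 fractions for the intermediate-risk volume; 66 Gy in 33 for regions at high risk. The section says the regimen should follow this table.
- Table 8, note b: "Please note all operated sites should receive 60 Gy".
- Table 2 (Section 7.1): "Low-risk participants: 2 Gy/day in 30 fractions for a total of 60 Gy", and 66 Gy in 33 fractions for high-risk participants. The text after the table also sets the dose at 60 Gy to at least 95% of the planning target volume.
- Schedule of Activities, Section 2.2: the same 60 Gy in 30 and 66 Gy in 33.
- Table 10 (Section 9.1.10.1.2.1): median dose within 2% of 60 Gy for PTV_6000 and within 2% of 66 Gy for PTV_6600.
- Section 9.1.10.1.2 again: post-surgical radiotherapy lasts 6 to 6.5 weeks at 5 fractions a week.

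**The concern.** A boost that brings 54 Gy up to 60 Gy cannot also bring 50 Gy up to 60 Gy. Table 8 allows 50 Gy as a sequential starting dose, so the combination is open to a site. The sentence is an operative dosing instruction, worded more firmly than the simultaneous-integrated-boost paragraph that follows it. A site that took it literally from 50 Gy would under-dose the operated bed and, where the extra boost is used, the high-risk area. Both arms receive this radiotherapy, and for low-risk participants in Arm B it is the only adjuvant treatment. Correct delivery therefore matters to those patients and to the comparator.

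**Working it through.** **Inputs.** Starting doses, boosts and 2 Gy fraction size: Section 9.1.10.1.2. Required totals: Tables 2 and 8. Median limits: Table 10. Compliance bands: Table 11. Treatment duration: Section 9.1.10.1.2.

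**Totals.** Bed dose = start + 6 Gy; high-risk dose = bed dose + 6 Gy. Each boost adds 3 fractions.

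| Start | Operated bed | High-risk area | Agrees with Table 8? |
|---|---|---|---|
| 54 Gy / 27 | 54 + 6 = 60 Gy / 30 | 60 + 6 = 66 Gy / 33 | Yes |
| 50 Gy / 25 | 50 + 6 = 56 Gy / 28 | 56 + 6 = 62 Gy / 31 | No |

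The 54 Gy row reproduces the protocol's own figures, so the fault is confined to the 50 Gy row.

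**Shortfall from 50 Gy.** Operated bed: (60 − 56)/60 = 4/60 = 6.7%. High-risk area: (66 − 62)/66 = 4/66 = 6.1%. Each course is 2 fractions short.

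**Boost needed from 50 Gy.** 60 − 50 = 10 Gy; 10/2 = 5 fractions. Then 25 + 5 = 30 fractions, and a further 6 Gy in 3 gives 66 Gy in 33.

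**Table 10 medians.** Lower limits are 60 × 0.98 = 58.8 Gy and 66 × 0.98 = 64.68 Gy. The totals of 56 and 62 Gy lie below them. To meet the limits, the plan median would have to be 58.8/56 = 105.0% or 64.68/62 = 104.3% of the delivered dose.

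**Duration.** 28/5 = 5.6 weeks, shorter than the stated 6 to 6.5 weeks. The 31-fraction course takes 31/5 = 6.2 weeks and falls inside that range, so duration would expose the 56 Gy course but not the 62 Gy one.

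**Table 11, prescription-dose row.** Per protocol means within 5%. The acceptable-variation entry reads "Delivered daily or total dose to any PTV differs from the protocol specified dose by 6-10" percent, and the unacceptable category starts above 10%. Shortfalls of 6.7% and 6.1% are both acceptable variations.

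**Other readings of the sentence.** If the 6 Gy boost belongs only to the 54 Gy option, the 50 Gy option has no stated boost and ends 10 Gy short. If 50 Gy is only the dose to the non-dissected neck, the operated bed still needs 10 Gy after that first phase, and the sentence supplies 6. No reading reaches 60 Gy from 50 Gy.

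**The case against.** The best defence is that the intended totals are not in doubt. Table 8, its note b, Table 2 and the text after it, the Schedule of Activities and the naming of the target volumes by dose all point to 60 and 66 Gy. A 56 Gy plan would breach note b and the stated duration within the same section, so a site could not claim full compliance with that section by following the one sentence. Sites are credentialed, and plans go to the radiotherapy vendor for approval before treatment. The RT QA Manual, which is not among the documents, may already have this right. All of this stands, and it limits the likely harm. It does not make the sentence correct.

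The defence also disposes of some stronger inferences about dose compliance:

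- **Unacceptable deviation.** A reader might apply the Table 11 uniformity criterion, "Dose to 95% of any PTV <90% of the prescribed dose", using 60 or 66 Gy as the reference. If D95% is 95% of the delivered dose, this gives 0.95 × 56/60 = 88.7% and 0.95 × 62/66 = 89.2%, both below 90%. That row refers to the prescribed dose, however, and a plan prescribed to 56 Gy would naturally be scored against 56 Gy. The percentages need both an assumed reference dose and an assumed D95%.
- **Missed D95% objectives.** Limits of 57.0 and 62.7 Gy might be read into Table 10. Its D95% column is relative to planned dose; only the median column is in absolute Gy.

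**Conclusion.** The point holds as a minor error in a treatment instruction. From the 50 Gy start the sentence gives 56 Gy in 28 fractions and 62 Gy in 31, each 4 Gy below the required total and below the Table 10 median limit. The sums need no assumption beyond the stated doses and fractions. The Table 10 comparison takes the plan median to be close to the delivered dose.

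Three trial-level conclusions that a reader might draw are not supported:

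- **Number affected.** The documents do not say how many plans used the 50 Gy start. With vendor review in place, the number may be zero.
- **Bias between arms.** Treatment is open-label, so differential use of the 50 Gy start is conceivable, but nothing in the documents suggests it. Arm A planning is tied to disease extent before neoadjuvant treatment regardless of response, which limits one route to a difference. No effect on EFS can be computed.
- **Shortfalls going unreported.** Section 10.12 states: "Extent of exposure for a participant is defined as number of cycles in which the participant receives the study treatment infusion". Delivered radiotherapy dose is therefore outside that summary. Section 10.11, however, commits to reporting any departure from protocol-directed administration, so it does not follow that a shortfall would go unreported.

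**What to change.** Reword the sequential-boost sentence along these lines: 50 Gy in 25 fractions then 10 Gy in 5 fractions, or 54 Gy in 27 fractions then 6 Gy in 3 fractions, giving 60 Gy in 30 fractions either way; if high-risk areas need an additional boost, a further 6 Gy in 3 fractions, giving 66 Gy in 33. Check that the RT QA Manual says the same. The simultaneous-integrated-boost paragraph needs no change.

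Optionally, ask the radiotherapy vendor to search the plans it already holds for courses of 28 or 31 fractions. Section 10.1 describes the 714 participants as already enrolled, so some courses may have been planned under the present wording, and this query would settle whether anyone was affected.

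The cost is one corrected sentence, one manual check and, if wanted, one data query. Endpoints, sample size and efficacy analyses are unchanged.

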9.1.10.1.3 Cisplatin

Three doses of cisplatin will be administered to those participants, in both treatment arms, considered at high-risk of recurrence based on the pathological features ie, positive margins (< 1 mm) or extranodal extension in the surgical specimen assessed by the local pathologist. If there are delays in cisplatin treatment, cisplatin may be administered up to 1 week following completion of RT. Participants that deviate from receiving planned cisplatin due to medical considerations may continue on the study after discussion with Sponsor and review of dose modification options (see Section 7.2.3). Three doses of cisplatin are permitted in those participants that do not undergo planned surgery and proceed directly to salvage CRT.

Cisplatin will be administered after all procedures and assessments are completed according to the Schedule of Activities in Section 2.0.

Cisplatin is given as a dose of 100 mg/m² using an infusion duration of 60 minutes (or infusion duration according to local practice).

Note: For body surface area over 2 m^2 the cisplatin dose will be capped at the one calculated for body surface area = 2 m^2 .

Before and after administration of cisplatin, adequate hydration is required and can be given as normally used in each institution. It is advised that participants can be hospitalized for at least 24 hours to allow optimal hydration before and after drug injection, if required per local regulations; or cisplatin may be administered on an outpatient basis, if adequate hydration can be managed and if allowed per local regulations. If hydration is performed as a planned hospitalization, it would not meet that criterion for SAE.

Administration of Cisplatin

The administration of cisplatin can follow the standard local practice and/or international guidelines. However, it is highly recommended to follow the instructions as reported below.

It is recommended that cisplatin start on the first day of RT (± 2 days). Follow local product label and institutional guidelines. Cisplatin can be administered up to 1 week following completion of RT regimen.

Before starting the treatment with cisplatin, the following criteria must be met:

- Neutrophils: $\geq 1.0 \times 10^9/\text{L}$
- Platelets: $\geq 75 \times 10^9/\text{L}$
- Creatinine clearance: $\geq 60 \text{ mL/min}$ (Cockcroft-Gault formula). It is recommended that participants whose creatinine clearance is $<60 \text{ mL/min}$ on the scheduled day of cisplatin administration receive IV fluid hydration for 1 to 2 days followed by a repeat CrCL. The cisplatin can be dosed based on the follow up CrCl level (see [Table 6](#)).

Recommendations:

- Encourage the participant to drink 2 to 3 liters of water per day during the days preceding and following cisplatin infusion.
- Any pre-existing dehydration must be corrected before starting the hydration related to cisplatin administration.
- Assess the hydration status during physical examination.
- Antiemetic medications should include:
 - serotonin type 3 antagonist (eg, granisetron 1-3 mg IV or ondansetron 8-32 mg IV or palonosetron IV 0.25 mg IV; 30 minutes before cisplatin infusion),
 - aprepitant (eg, 125 mg orally [per os; po] 30 minutes before cisplatin infusion and 80 mg/day PO during the 2 following days, or 150 mg IV on Day 1),

- corticosteroids (eg, dexamethasone 20 mg [12 mg if given with aprepitant] 30 minutes before cisplatin infusion and dexamethasone 8 mg twice per day [8 mg once per day if given with aprepitant] po during the 3 following days). Another equivalent corticosteroid regimen is allowed according to local practice. The maximum dose of steroids for antiemetic treatment or prophylaxis is 20 mg/day [12 mg if given with aprepitant] dexamethasone or its steroid equivalent),
- any "as-needed" antiemetics according to each institutional guideline (metoclopramide, alizapride, additional steroids, etc.).
- Intravenous pre- and post-hydration per local guidelines. Following cisplatin infusion, an overnight additional hydration is also allowable, per local regulations.
- Cisplatin infusion: mannitol before cisplatin infusion is allowed according to local practice. Cisplatin should be prepared according to local practice and should be infused over 60 minutes.
- Urinary output: >100 mL/hour before starting cisplatin infusion and also after cisplatin infusion during at least 4-6 hours (400 mL/4 hours). If this level is not reached, furosemide (LASIX® [furosemide, Sanofi Aventis]) 20 mg IV should be given.
- Participants may be weighed before and after cisplatin infusion, if weight gain furosemide (LASIX®) could be given.
- Replace potassium and magnesium as needed.
- Check for presence of ototoxicity.

9.1.10.2 Surgery Guidelines

9.1.10.2.1 Pre-operative Assessment

Preoperative assessment should proceed as per institutional guidelines and participant's Charlson co-morbidity index, ASA-score, and nutritional status are recommended to be assessed. Also routine hematology and chemistry tests will be performed as detailed in Section 2.0 – Schedule of Activities. Preoperative imaging should be performed as described in Section 2.0 - Schedule of Activities and Section 9.2.1 - Tumor Imaging and Assessment of Disease. In case of procedures with potential long-term swallowing compromise the treating surgeon may obtain pulmonary function tests or a barium swallow as per local SoC. Surgeons are recommended to document the primary tumor and lymphadenectomy surgical plan at initial evaluation. This may include either photo documentation or appropriate drawings to identify the planned surgical margin of resection (in case of tumor response with intervention).

